### **7.2.5 Pharmacokinetic and pharmacodynamic assessments**

#### **7.2.5.1 Pharmacokinetic assessments**

PK samples will be collected at the times indicated in the SoA [Table 2].

The date and actual time of collection of each blood sample will be entered in the eCRF. In addition, the food status will be recorded in the eCRF for study treatment intake on Day 1 and at Month 2.

The allowed time deviation from scheduled post dose PK sampling time points is listed as follows:

Time point	Allowed time window
1-12 hours post dose	±3 min
24 hours post dose	+18 min (Must obtained before the next dosing)

Details about the collection, sampling, storage, and shipment procedures can be found in the laboratory manual.

The analysis of cenerimod in plasma will be performed by a laboratory approved by the Sponsor using a validated bioanalytical method.

The PK data generated from this study may be used for PPK modeling in future.

#### **7.2.5.2 Pharmacodynamic assessments**

The PD marker is total lymphocyte counts, which will be measured as part of the hematology tests [see Section 7.2.3.4].

### **7.2.6 Biomarker assessments**

#### **7.2.6.1 Disease activity biomarkers**

Serum, EDTA plasma, and whole blood (PAXgene) samples will be drawn at the indicated visits [Table 1, Table 2, and Table 3]. The sample collection date will be recorded in the eCRF.

Details of the collection, labeling, and shipment of the samples can be found in the laboratory manual provided to the investigator.

The following biomarkers will be measured at a central laboratory as per the SoA:

- Whole blood will be collected in PAXgene tubes to measure the overexpression of mRNA of specific IFN-1 inducible genes. Other gene expression signatures will be reported to examine T and B cell function, metabolism, and mRNA production.
- In serum samples: ANA, anti-dsDNA, anti-Sm, CH-50, and complement C3 and C4.
- In EDTA plasma samples: IFN alpha levels.

Details of the collection, labeling, and shipment of the samples can be found in the laboratory manual provided to the investigator.

## **8 SAFETY DEFINITIONS AND REPORTING REQUIREMENTS**

### **8.1 Safety definitions**

#### **8.1.1 Definition of adverse events**

An AE is any untoward medical occurrence, i.e., any unfavorable and unintended sign, including an abnormal laboratory finding, symptom, or disease that occurs in a participant during the study, whether or not considered by the investigator/delegate as related to study treatment.

AEs include:

- Exacerbation of a pre-existing disease if considered medically relevant.
- Exacerbation of a pre-existing disease except for efficacy endpoints and associated symptoms.
- Increase in frequency or intensity of a pre-existing episodic disease or medical condition.
- Disease or medical condition detected or diagnosed during the study after signing the ICF, even though it may have been present prior to the start of the study.
- Continuous persistent disease or symptoms present at study start that worsen after the start of the study.
- Abnormal change in physical examination or ECG findings, if they represent a clinically significant finding that was not present at study start or worsened during the study as per investigator medical assessment.
- Laboratory test abnormalities if they represent a clinically significant finding (symptomatic or not) that was not present at study start or worsened during the study as per investigator judgment, led to interruption or permanent discontinuation of study treatment.

### **8.1.2      Definition of adverse events of specific interest**

AESIs will include the anticipated risks of treatment with cenerimod or the known class effects or the events that may be related to SLE comorbidities (e.g., cardiovascular AEs) and will address the following safety areas:

- Effect on HR and rhythm-related AEs
- Hypotension-related AEs
- Hypertension-related AEs
- Cardiovascular-related AEs
- Hepatobiliary disorders / liver enzyme abnormality-related AEs
- Pulmonary-related AEs
- Eye disorder-related AEs
- Infection-related AEs

- Skin malignancy-related AEs
- (Non-skin) malignancy-related AEs

A list of AESIs (MedDRA preferred terms) will be defined in the SAP.

### **8.1.3 Definition of serious adverse events**

An SAE is defined by the ICH guidelines as any AE fulfilling at least 1 of the following criteria:

- Fatal.
- Life-threatening: Refers to an event in which the participant was at risk of death at the time of the event. It does not refer to an event that hypothetically might have caused death had it been more severe.
- Requiring in-patient hospitalization (i.e., the AE required admission to hospital) or prolongation of existing hospitalization.
- Resulting in persistent or significant disability or incapacity.
- Congenital anomaly or birth defect.
- Medically significant: Refers to important medical events that may not immediately result in death, be life-threatening, or require hospitalization, but may be SAEs based upon appropriate medical judgment, as they may jeopardize the participant, and/or may require medical or surgical intervention to prevent 1 of the outcomes listed in the definitions above.

The following reasons for hospitalization are not considered as SAEs:

- Hospitalization for cosmetic elective surgery, or social and/or convenience reasons.
- Hospitalization for pre-planned (i.e., planned prior to signing the ICF) surgery or standard monitoring of a pre-existing disease or medical condition that did not worsen, e.g., hospitalization for coronary angiography in a participant with stable angina pectoris.

### **8.1.4 Intensity of adverse events**

The intensity of AEs is graded on a 3-point scale—mild, moderate, severe—as follows:

- Mild
  - The event may be noticeable to the participant. It does not usually influence daily activities, and normally does not require intervention.
- Moderate

- The event may make the participant uncomfortable. Performance of daily activities may be influenced, and intervention may be needed.
- Severe
  - The event may cause noticeable discomfort and usually interferes with daily activities. The participant may not be able to continue in the study, and treatment or intervention is usually needed.

A mild, moderate, or severe AE may or may not be serious [see Section 8.1.2]. These terms are used to describe the intensity of a specific event. Medical judgment should be used on a case-by-case basis.

### **8.1.5 Relationship to study treatment**

Each AE/SAE must be assessed by the investigator/delegate as to whether there is a reasonable possibility of causal relationship to the study treatment and reported as either related or unrelated.

### **8.1.6 Relationship to study design or protocol-mandated procedure**

An AE/SAE is defined as related to the study design or protocol-mandated procedure if it appears to have a reasonable possibility of a causal relationship to either the study design or to a protocol mandated procedure.

Determining the likelihood that a protocol-mandated procedure caused the AE/SAE will be provided by the investigator/delegate.

### **8.1.7 Definition of study treatment overdose, misuse, and abuse**

Study treatment overdose is defined as higher than the dose of study treatment prescribed.

Study treatment misuse is defined as any intentional and inappropriate use of the study treatment which is different from the instruction provided in the protocol.

Study treatment abuse is defined as any intentional and excessive use of the study treatment, with harmful physical or psychological effects.

In the event of a study treatment overdose, abuse, or misuse, the investigator/delegate must contact the sponsor and closely monitor the participant for any AEs/SAEs.

## **8.2 Reporting procedures**

### **8.2.1 Reporting adverse events**

The occurrence of an AE may come to the attention of study personnel during study visits, telephone calls, or interviews with participants presenting for medical care.

At each study visit (scheduled or unscheduled), the investigator/delegate will inquire about the occurrence of AEs since the last visit.

All AEs with an onset date after signing the ICF and up to 6 months after study treatment discontinuation must be recorded in the eCRF.

The AE should be reported as a final diagnosis (if possible) rather than a list of symptoms.

Information to be collected on an AE form in the eCRF includes date of onset, action taken with the study treatment (e.g. dose reduction or suspension), outcome of AE, date of resolution (if applicable), and investigator/delegate's assessment of intensity as well as relationship to study treatment, study design or protocol-mandated procedures.

Information on worsening of intensity will be collected on a new AE form. If the AE lessens in intensity, no change in the severity is required to be reported.

AEs still ongoing after study treatment discontinuation must be followed up until resolution, until they are no longer considered clinically relevant, or until stabilization.

### **8.2.2 Reporting serious adverse events**

All SAEs must be reported by the investigator/delegate to the sponsor's Drug Safety department within 24 h of site staff first becoming aware of the event.

All SAEs occurring after signing the ICF and up to 6 months after study treatment discontinuation must be recorded on an SAE form, regardless of the investigator-/delegate -attributed causal relationship with study treatment or study -mandated procedures.

The SAE forms must be sent to the sponsor's Drug Safety department (see contact details on the SAE form). The investigator/delegate must complete the SAE form in English and must assess the event's causal relationship to the study treatment.

Any relevant information from source documents regarding the SAE, e.g., hospital notes or discharge summaries, etc., must be summarized on the SAE form.

Follow-up information about a previously reported SAE must be promptly reported. The sponsor's Drug Safety personnel may contact the investigator/delegate to obtain further information.

If the participant is hospitalized in a hospital other than that of the study site, it is the investigator/delegate's responsibility to contact this hospital to obtain all SAE -relevant information and documentation.

New SAEs occurring after the 6-month follow-up period must be reported to the sponsor's Drug Safety department within 24 h of site staff first awareness/knowledge of the event, **only** if considered by the investigator/delegate to be causally related to previous exposure to the study treatment.

SAEs still ongoing after study treatment discontinuation must be followed up until resolution, stabilization, or until the event outcome is provided.

### **8.2.3 Reporting procedure for SUSARs**

The expectedness of an SAE is determined by the sponsor according to the reference safety information section provided in the Investigator's Brochure.

Any SAE that is assessed as related and unexpected against the reference safety information is considered a SUSAR.

Any SUSAR must be reported by the sponsor/CRO to relevant health authorities, and investigators. Submission to central/local IECs/IRBs will be done as per their requirements.

### **8.2.4 Reporting medical or surgical intervention**

At each study visit (scheduled or unscheduled), the investigator/delegate will inquire about any medical or surgical intervention performed on the participant.

All medical or surgical intervention with an onset date after signing the ICF and up to 6 months after study treatment discontinuation must be recorded in the eCRF.

## **8.3 Pregnancy**

If a woman becomes pregnant while on study treatment, study treatment must be discontinued [see Section 5.8.1.2]. The investigator/delegate must counsel the participant and discuss the risks of continuing with the pregnancy and the possible effects on the fetus.

### **8.3.1 Reporting of pregnancy**

Any pregnancy occurring in a female participant after signing of the ICF and up to 6 months following study treatment discontinuation must be reported to the sponsor's Drug Safety department within 24 h of site staff first becoming aware of the event.

All pregnancies must be reported on the sponsor's Pregnancy form, which is sent to the sponsor's Drug Safety department (see contact details provided on the Pregnancy form).

The investigator/delegate must complete the Pregnancy form in English.

### **8.3.2 Follow-up of pregnancy**

Any pregnancies must be followed up to their conclusion and the outcome must be reported to the sponsor's Drug Safety department. If local regulations or IRB/EC decisions mandate the reporting of the baby's health after delivery, this will be performed using the same procedure in Section 8.3.1. Any AE associated with the pregnancy of a female participant occurring during the AE reporting time must be reported on separate AE forms in the eCRF as described in Section 8.2.1.

Any SAE occurring during the pregnancy must be reported on an SAE form as described in Section 8.2.2.

## **9 STATISTICAL METHODS**

All statistical analyses will be conducted by the sponsor/CRO.

The SAP will provide full details of the analyses, data displays, and algorithms to be used for data derivations.

### **9.1 Analysis sets**

#### **9.1.1 Screened set**

The screened set includes all participants who provided informed consent and participated in any screening procedures.

#### **9.1.2 Safety Analysis Set (SS)**

The SS includes all participants who received at least 1 dose of study treatment.

#### **9.1.3 Pharmacokinetic Analysis Set (PKS)**

The PKS includes all participants from the SS who, after initiation of cenerimod treatment, have at least one PK sample collected, had evaluable plasma concentrations, and did not deviate from the protocol in a way that might affect the evaluation of the PK endpoint.

#### **9.1.4 Pharmacodynamic Analysis Set (PDS)**

The PDS includes all participants from the SS who, after initiation of cenerimod treatment, have at least one PD sample collected, had evaluable total lymphocyte counts, and did not deviate from the protocol in a way that might affect the evaluation of the PD endpoint.

### **9.2 Description of statistical analyses**

All available data (regardless of whether collected during scheduled or unscheduled visits) for each participant will be used in all statistical analyses unless otherwise specified.

### **9.2.1 Analysis of safety endpoints**

Descriptive analysis of safety endpoints will be performed using the SS (see definition in Section 9.1.2).

If not otherwise stated, only treatment-emergent safety data will be considered in tables and figures. Treatment-emergent safety data will be defined as assessments (or events) that were performed (or started) on or after the first study treatment intake (inclusive) up to the last study treatment intake + 180 days (inclusive).

Analyses on marked abnormalities for ECG and laboratory variables and Notable BP abnormalities will be specified in the SAP.

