## 1 PROTOCOL SUMMARY

### 1.1 Protocol synopsis ID-064A204

TITLE	A multicenter, open label, single arm, multiple-dose study to evaluate the safety, tolerability, pharmacokinetics and pharmacodynamics of cenerimod in adult Chinese participants with moderate-to-severe systemic lupus erythematosus (SLE) on top of background therapy
OBJECTIVES	
Primary objectives
 

• To evaluate the safety and tolerability of cenerimod 4 mg in Chinese participants.

• To evaluate the PK of cenerimod 4 mg in Chinese participants.

• To evaluate the PD of cenerimod 4 mg in Chinese participants.

 
Other objective
 

• To preliminarily evaluate the efficacy of cenerimod 4 mg in Chinese participants.

ENDPOINTS	
Safety endpoints
 
The following endpoints will be evaluated.
 

• Occurrence of treatment-emergent adverse events (AEs), serious AEs (SAEs) and AEs of special interest (AESIs)

• Occurrence of AEs leading to permanent discontinuation of study treatment.

• Changes in vital signs (systolic blood pressure [SBP], diastolic blood pressure [DBP]) and body weight from baseline to each post-baseline assessment.

• Changes in hourly 12-lead electrocardiogram (ECG) variables (hear rate [HR] and the QTcB and QTcF intervals) and SBP/DBP assessments at Day 1 cardiac monitoring.

• Changes in 12-lead ECG variables (HR and the PR, QRS, QTcB, and QTcF intervals) from baseline to each post-baseline assessment.

• Treatment-emergent medically relevant ECG abnormalities from baseline to each post-baseline assessment.

- Changes in laboratory variables (hematology, blood chemistry, and urinalysis) from baseline to each post-baseline assessment.
- Treatment-emergent marked laboratory abnormalities from baseline to each post-baseline assessment.

The treatment-emergent period for the study is defined as the time from first study treatment intake until the end of the safety follow-up period, i.e., up to last study treatment intake + 180 days.

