		6 months			NA	
VISITS	Number	15	16, 17, 18, 19	20 (FSV)	U1, U2, ...	RI
	Name	FU1	FU2, FU3, FU4, FU5 Phone call	Final study visit	Unscheduled 	Re-initiation
	Time window	1 month after last study treatment intake ( $\pm 7$ days)	Monthly after FU1 ( $\pm 7$ days)	6 months after last study treatment intake ( $\pm 7$ days)	Any day between ICF signature and FSV (assessments to be performed as applicable)	Re-initiating study treatment after interruption lasting more than 7 days between Day 1 and Day 14
To be performed at all visits						
SAEs/AEs 		X	X	X	X	X
To be performed at specific visits						
SLE and concomitant therapies		X	X	X	X	X
Physical examination 		X		X	X	X
Body weight 				X	X	
mSLEDAI-2K, BILAG, SFI, PGA, CLASI, Tender/swollen joint count					X	
Vital signs, 12-lead ECG 		X		X	X	X 
Ophthalmological examinations				X	X	
OCT					X	
Labs (hematology/blood chemistry  , urine analyses) 		X		X	X	
Labs (coagulation) 					X	
BILAG associated blood and urine samples (anti-cardiolipin, lupus anticoagulant, haptoglobin, and Coombs) 					X	
Serum pregnancy test 				X	X	
Urine pregnancy test 		X	X			
Viral serology / TB test					X	
PK sampling				X		

PERIODS	Name	FOLLOW-UP 			UNSCHEDULED	
		Duration	6 months		NA	
VISITS	Number	15	16, 17, 18, 19	20 (FSV)	U1, U2, ...	RI
	Name	FU1	FU2, FU3, FU4, FU5 Phone call	Final study visit	Unscheduled 	Re-initiation
	Time window	1 month after last study treatment intake ( $\pm 7$ days)	Monthly after FU1 ( $\pm 7$ days)	6 months after last study treatment intake ( $\pm 7$ days)	Any day between ICF signature and FSV (assessments to be performed as applicable)	Re-initiating study treatment after interruption lasting more than 7 days between Day 1 and Day 14
SLE biomarkers in PAXgene samples				X	X	
IFN-alpha sample				X	X	
Anti-dsDNA, complement (C3, C4, CH50)				X	X	
ANA				X	X	
Anti-Smith				X	X	
Study treatment dispensing/return and accountability						X

One month is considered to be 30 days.

Day 1 is to be used as the reference date for the purpose of calculating the subsequent visit dates (and time windows).

\* Study treatment should not be taken before the assessment (i.e., SBP/DBP, ECGs, laboratory tests and PK sampling).

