#### 4.1.1 Study periods for an individual participant

The screening period will last up to 30 days. Participants will receive cenerimod for a maximum of 12 months. For participants that permanently discontinue study treatment, they will enter the post-treatment observation period. Participants that complete the 12-month treatment period will enter a 6-month safety follow-up period until FSV.

**Post-treatment observation period** (only applicable to participants who permanently discontinue study treatment): starts the day after the last dose of study treatment and participants will complete visits until at least 6 months after last study treatment intake as follows:

- Participants who permanently discontinue study treatment before or at Month 6 will complete study visits until Month 12 and the FSV will be at Month 12 (i.e., PTOP Visit 14).
- Participants who permanently discontinue study treatment between Month 7 and Month 12 (inclusive) will complete PTOP FU visit(s) until 6 months after last study treatment intake and the FSV will be one of the monthly PTOP FU visits, as applicable.

**Follow-up period:** Starts on the day after the last dose of study treatment and ends 6 months, i.e., 180 days, thereafter with FSV.

A participant's participation in the study ends with the completion of the FSV. The participant will participate in the study for a duration of up to 19 months.

The visit schedule and protocol-mandated procedures are performed according to the SoA [Table 1, Table 2, and Table 3] and are described in Section 7.2.

The study design is depicted in Figure 1.

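### The treatment-emergent window closes 180 days after the last dose, but the 6-month final visit is on time up to day 187, so a compliant visit on days 181–187 can drop out of the safety abnormality tables

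*Combined protocol and SAP*

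**What the plan says.** Section 9.2.1 sets a default rule: "If not otherwise stated, only treatment-emergent safety data will be considered in tables and figures". It defines such data as assessments performed, or events started, "on or after the first study treatment intake (inclusive) up to the last study treatment intake + 180 days (inclusive". The synopsis (Section 1.1) treats this cut-off as the close of follow-up; its treatment-emergent period runs "until the end of the safety follow-up period, i.e., up to last study treatment intake + 180 days". Section 4.1.1 says the same of the follow-up period: "Starts on the day after the last dose of study treatment and ends 6 months, i.e., 180 days, thereafter with FSV".

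Table 2 places Visit 20, the FSV, at "6 months after last study treatment intake" with a window of ±7 days, and its notes add "One month is considered to be 30 days". Hematology, chemistry, urinalysis, vital signs, 12-lead ECG and body weight are all due at that visit.

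Two other places bear on the point. Table 5 and Section 9.2.1 label marked laboratory, medically relevant ECG and notable BP abnormalities as treatment-emergent. Section 9.2.1 also says that the by-visit summaries of vital signs, weight, ECG and laboratory values cover every scheduled visit after baseline.

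**The concern.** A visit held on day 183 after the last dose complies fully with Table 2, yet lies outside the window that decides what is tabulated. No passage extends the window to cover the seven days of tolerance. A marked liver-test or ECG abnormality found that day would not be counted, while the same finding on day 179 would be. The difference would come from the appointment date alone.

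For completers, follow-up visits FU2–FU5 are telephone calls. After FU1, the FSV is therefore the only scheduled assessment of chemistry, urinalysis, ECG and BP. Weight is routinely entered in the eCRF only at Visits 1, 14 and 20. Safety is a primary objective and about 15 participants are planned, so a few missing records would visibly change a row.

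**Working it through.** **Inputs**
- Month length: 30 days (Table 2 notes).
- FSV: 6 months after last intake, ±7 days (Table 2).
- Cut-off: last intake + 180 days, inclusive (Section 9.2.1).
- Sample size: approximately 15 (Section 9.4).
- Distribution of FSV dates within the window: not given, so assumed below.

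**The plan's own figure.** 6 × 30 = 180 days, which reproduces the stated cut-off.

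**Overlap with the visit window**
- Permitted days: 180 − 7 = 173 to 180 + 7 = 187, which is 15 days.
- Inside the cut-off: days 173–180, 8 days.
- Outside: days 181–187, 7 days.
- Share of permitted days outside: 7/15 = 46.7%.

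**From permitted days to visits.** For timing symmetric about day 180, the share of late visits is (1 − p)/2, where p is the proportion held exactly on day 180.

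| Assumed timing | Share of FSVs on days 181–187 | Expected of 15 completers |
|---|---|---|
| Even over 15 days (p = 1/15) | 46.7% | 7.0 |
| Normal, SD 4 days, cut at ±7 | 45% | 6.7 |
| Normal, SD 3 days, cut at ±7 | 43% | 6.5 |
| Normal, SD 2 days, cut at ±7 | 40% | 6.0 |
| 25% exactly on day 180 | (1 − 0.25)/2 = 37.5% | 5.6 |
| 50% exactly on day 180 | (1 − 0.50)/2 = 25% | 3.8 |
| 75% exactly on day 180 | (1 − 0.75)/2 = 12.5% | 1.9 |
| None late | 0% | 0 |

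The logical ceiling is 100%, if every visit is late but on schedule. In the 12.5% row, the chance that at least one of 15 completers is affected is 1 − 0.875^15 ≈ 87%. The last column and this probability assume that all 15 complete.

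**Early discontinuers.** Participants who stop at or before Month 6 have their FSV at Month 12, Day 360 ± 7 counted from Day 1 (Section 4.1.1, Table 3). The earliest permitted day is 353. If the last dose is on day L, every permitted day is beyond the cut-off when 353 − L > 180, that is, when L < 173.
- Last dose on Day 30: 323–337 days after it.
- Last dose on Day 90: 263–277 days.
- Last dose on Day 150: 203–217 days.
- Last dose on Day 180: 173–187 days, so again 7 of 15 permitted days are outside.

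**Effect of a +187-day limit.** For the 6-month FSV, 0 of 15 permitted days would remain outside. The Month 12 FSV of most early discontinuers would still be outside.

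**The case against.** The strongest reply is that the default rule gives way where the text states otherwise, and the by-visit summaries are stated to cover every scheduled visit after baseline. Visit 20 is one of these. Table 5 also carries adverse events through to the FSV. This stands in part: a reader might infer that the final-visit row disappears from all safety tables, and the documents do not establish that. Nor do they say that the by-visit wording overrides the filter, so two programmers could produce different tables. The reply is weakest for abnormality displays explicitly called treatment-emergent. The general instruction in Section 9.2 to use all available data does not settle it, because it yields to more specific rules.

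A reader might also infer that evidence of recovery after stopping the drug is lost. That goes too far. Lymphocyte counts by visit are analysed under Section 9.2.3, outside the safety filter. FU1 is itself one month off drug, and early discontinuers have laboratory tests and ECGs at their post-treatment observation visits (Table 3).

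The claim that about half of visits will be affected needs an even spread of dates. The documents give none, and Section 7.1 asks sites to keep participants on schedule.

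A fixed 180-day limit is defensible for adverse events, because Section 8.2.1 records them for 6 months after discontinuation. This stands and limits the fix. Finally, the protocol defers derivations and the abnormality analyses to a separate SAP that is not in the available text and might resolve the matter. Until it does, the written definition governs.

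**Conclusion.** The mismatch holds on the protocol's own figures: 7 of the 15 days on which a 6-month FSV is compliant lie outside the treatment-emergent window. It is clearest for the marked laboratory, medically relevant ECG and notable BP abnormality displays. For by-visit summaries it is an unresolved conflict of wording. The symmetric scenarios with some late visits put the affected share between 12.5% and about 47%. It is zero if nobody is late, and the documents do not allow a choice among these values.

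Severity is minor. The records are still collected, the rule restricts tables and figures and does not mention listings, and Section 7.2.3.4 requires clinically relevant laboratory abnormalities to be reported as adverse events. No test, power calculation or sample size depends on the window.

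**What to change.** In Section 9.2.1, and correspondingly in the synopsis and SAP:

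- State that laboratory, ECG, BP and weight assessments from the scheduled 6-month FSV, if done within its permitted window (up to last intake + 187 days), count as treatment-emergent and enter both the by-visit and the abnormality tables.
- Keep the adverse-event window at 180 days, in line with Section 8.2.1, or amend both together. Either way, reconcile it with the Table 5 wording that carries adverse events to the FSV.
- State how post-treatment observation assessments beyond last intake + 180 days are displayed, including the Month 12 FSV of participants who stop before about Month 6. A separate off-treatment summary would serve.

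The cost is a short wording change, with no new visit, procedure or data. The Version 3.0 amendment details report no participants enrolled, so at that version it could be made prospectively. The downside is an assessment window up to seven days longer for some participants than for others.
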